3.8. Outcome Data collection

RCT outcome measures

1. Quality of life as measured by the Kidney Disease Quality of Life instrument – Short Form (KDQOL-36TM)⁴⁰
2. Degree of cognitive impairment as measured by the Isaacs Set Test (IST 15)⁴¹
3. Degree of anxiety, depression, well-being, functioning and risk as measured by the Clinical Outcomes in Routine Evaluation measure (CORE 34)⁴²
4. The degree to which the patient felt that they had shared in decision-making about their care as measured by the Patient Experience of Shared Decision Making (SHARED) instrument⁴³
5. Agreement between the patient and their nominated relative/friend in terms of the patient's preferences. We will measure this by asking the carer to make an independent assessment of the patient's preferences in relation to the key information covered by the ACP intervention (a-e above), before taking part in the ACP.
6. An economic evaluation of costs and benefits of the ACP intervention will be conducted utilising data collected from the following sources:
 - a. Electronic hospital admissions and outpatient data for each patient
 - b. Patient completed cost diaries documenting health and social care resource use
 - c. Patient quality of life data using the SF-12 (contained within the (KDQOL-36TM)⁴⁰)

Resource use will be valued according to appropriate tariffs, allowing comparison of mean costs per patient by group allocation for the 12 week period of the trial.

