4.2. Economic Evaluation

4.2.a. Outline of the economic analysis

The feasibility of a cost-effectiveness and cost-utility analysis of the ACP intervention compared to usual care, conducted from a societal perspective, will be explored in the pilot study, to inform a full economic evaluation alongside the main trial.

4.2.b. Outcomes for the analysis

The analysis will report the cost per [primary endpoint achieved e.g. relative/friend agreement or SHARED]; and the cost per quality adjusted life year (QALY) gained of the ACP intervention compared to usual care.

4.2.c. Participant utilities

The SF-6D preference based instrument contained within the SF-12 and KDQoL-36 survey will be administered to all patient participants at baseline and 12 weeks. QALY weights (utilities with a value between 0 and 1) from self-reported data will be calculated using UK tariffs (the value set) of the SF-6D. QALYs will be calculated by multiplying the utility with the time spent in that health state using an area under the curve approach. A minimally important difference in utility has been reported at 0.03-0.05. Mean costs (including volume of resource use) and mean health outcomes per allocated group will be reported with 95% confidence intervals. Mean costs will be presented as unadjusted and adjusted for any baseline differences in age, sex, or SES.

4.2.d. Detailed Statistical Analysis of Economic Data

Skewed cost data: Cost data are likely to be right skewed as they are bounded by zero (i.e. can't be negative); have no upper bound, and a small number of patients may incur very high costs, affecting

the mean. The cost distribution will be plotted in a histogram and non-parametric bootstrapping will be used for analysis.

Results: The mean and total volume of major categories of resource use (e.g. hospitalisations; doctor's visits; nurse visits;) will be reported for each group. The difference in the volume of resource use for each group and 95% confidence intervals for the difference will be reported.

Total costs: The total cost will be calculated by multiplying the arithmetic mean cost by the number of participants in each group. Mean costs with standard deviations and total costs for each group will be reported in UK pounds for the most recent reference year. The difference in total costs will be assessed using the student t test and/or analysis of variance (ANOVA). Total costs will also be adjusted for relevant baseline characteristics (e.g. age, sex).

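### Section 4.2.d attaches a t test and covariate adjustment to a group-level total cost with one value per arm, and the QALY comparison states no adjustment for baseline utility

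*Combined protocol and SAP*

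**What the plan says.** **Costs.** Section 4.2.d expects right-skewed costs and states: "The cost distribution will be plotted in a histogram and non-parametric bootstrapping will be used for analysis". It then defines the total: "The total cost will be calculated by multiplying the arithmetic mean cost by the number of participants in each group". Three statements follow about reporting, testing and adjustment:

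- On what is to be reported, the plan says: "Mean costs with standard deviations and total costs for each group will be reported in UK pounds for the most recent reference year"
- On the test to be used, it says: "The difference in total costs will be assessed using the student t test and/or analysis of variance (ANOVA"
- On covariates, it adds this sentence: "Total costs will also be adjusted for relevant baseline characteristics (e.g. age, sex"

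Section 3.8 describes the cost outcome differently, as "allowing comparison of mean costs per patient by group allocation for the 12 week period of the trial". Section 4.2.c plans mean costs by allocated group with 95% confidence intervals, both unadjusted and adjusted for baseline differences in age, sex or socio-economic status.

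**QALYs.** Under section 4.2.c the SF-6D "will be administered to all patient participants at baseline and 12 weeks", and "QALYs will be calculated by multiplying the utility with the time spent in that health state using an area under the curve approach". The only adjustments stated anywhere in section 4.2 are for costs. Section 4.1.b applies baseline-adjusted analysis of covariance to CORE 34, KDQOL-36 and SHARED; it does not name SF-6D utility or QALYs. The term *QALY gained* appears in section 4.2.b, where the comparison is with usual care, and again among the benefits listed in section 4.2.d, at 12 weeks, with no reference point given.

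**The concern.** A group mean multiplied by the group size is a single figure. It has no spread within the arm, and there are no patient records to which age or sex could be attached. A test and an adjustment specified on that figure cannot be carried out. The figure also depends on how many patients happen to be in each arm, which says nothing about the cost of care.

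For QALYs, the area under a two-point curve gives baseline utility the same weight as 12-week utility. Half of the outcome is therefore fixed before randomisation, and chance differences in it go straight into the unadjusted comparison as noise. The plan adjusts the parent instrument (KDQOL-36) for baseline but says nothing about the quantity derived from it.

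What is at stake is limited. Section 2.4 makes methods for assessing costs, benefits and cost-effectiveness an objective of this study, and section 4.2.a says the work is to inform a full economic evaluation. A method that cannot be run, or that wastes information already collected, could be carried into the main trial.

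**Working it through.** The plan gives no economic result or precision figure, so there is nothing to reproduce first.

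**Part (a): total cost**

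1. As defined there is one value per arm. Degrees of freedom = 1 + 1 - 2 = 0, so the t statistic and p-value are undefined.
2. With the patient as the unit: section 3.4 gives 40 patients and 25% attrition, so 40 × 0.75 = 30. Section 3.3 gives equal allocation, so 15 per arm. Degrees of freedom = 15 + 15 - 2 = 28, and covariates can be entered.
3. A mean × n total follows arm size. With identical mean costs and arms of 16 and 14, the totals differ by 16/14 - 1 = 14.3%.

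**Part (b): QALY difference**

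From the documents: 15 per arm as above; T = 12/52 = 0.2308 year; a minimally important utility difference of 0.03 to 0.05 (section 4.2.c). Assumed, because the documents give neither: the same utility SD at both times (0.10, range 0.08 to 0.15) and a baseline to 12-week correlation r of 0.3, 0.5 or 0.7. The figures are for patients with both utilities measured; they do not address deaths or dropout.

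Let u0 and u12 be the two utilities.

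- Area under the curve: QALY = T × (u0 + u12)/2
- Gain over own baseline: T × (u12 - u0)/2

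The variance of the difference between arms is (2/15) × T² × SD² times:

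- unadjusted area under the curve: (1 + r)/2
- unadjusted change from baseline: (1 - r)/2
- baseline-adjusted: (1 - r²)/4 × (1 + 1/26), the last term being the small-sample cost of estimating the slope (26 = 30 - 4)

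The ratios of standard errors are therefore sqrt((1 - r)/2) × 1.019 against the unadjusted area under the curve and sqrt((1 + r)/2) × 1.019 against change, where 1.019 = sqrt(1 + 1/26).

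| r | Ratio to unadjusted AUC | SE cut | Ratio to change | SE cut |
|---|---|---|---|---|
| 0.3 | 0.592 × 1.019 = 0.603 | 40% | 0.806 × 1.019 = 0.822 | 18% |
| 0.5 | 0.500 × 1.019 = 0.510 | 49% | 0.866 × 1.019 = 0.883 | 12% |
| 0.7 | 0.387 × 1.019 = 0.395 | 61% | 0.922 × 1.019 = 0.940 | 6% |

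Simulation of 20,000 trials with 15 per arm and SD 0.10 agrees with these ratios to within about 0.01.

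If the SDs are unequal (12-week SD 0.8 or 1.25 times the baseline SD, r = 0.5), the ratio to the unadjusted area under the curve is 0.44 or 0.55 before the small-sample term.

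The two outcome definitions differ only by T × u0. With u0 in the model, the arm coefficient is the same for both.

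**Remaining precision.** A utility difference d at week 12 from equal baselines is worth 0.5 × T × d: 0.0035 QALY for 0.03 and 0.0058 QALY for 0.05. The adjusted 95% half-width is 2.052 × T × SD × sqrt(2/15) × sqrt((1 - r²)/4) × 1.019, where 2.052 is the t value on 27 degrees of freedom.

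| Assumed SD | r = 0.3 | r = 0.5 | r = 0.7 |
|---|---|---|---|
| 0.08 | 0.0067 | 0.0061 | 0.0050 |
| 0.10 | 0.0084 | 0.0076 | 0.0063 |
| 0.15 | 0.0126 | 0.0114 | 0.0094 |

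**The case against.** **The cost wording is a slip, and the right analysis is already there.** This largely stands. Section 3.8 compares mean costs per patient. Section 4.2.c plans confidence intervals and an adjustment that need patient-level costs. Section 4.2.d itself plans standard deviations and a bootstrap. A reader might infer that the trial has no valid cost comparison; these passages show otherwise. What remains is that the one place where total cost is defined contradicts that intent, and that the section does not say whether the bootstrap or the t test governs.

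**The unadjusted QALY comparison is not biased.** This stands in full. A reader might infer bias from a chance baseline imbalance, but under randomisation the unadjusted difference is unbiased on average. The case for adjustment is precision.

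**QALY gained is not really ambiguous.** This mostly stands. The only calculation rule given is area under the curve and the only stated comparison is with usual care; no passage subtracts baseline utility. Utilities can be invented for which the two readings have opposite signs, but the documents do not support treating this as two competing analyses. The item at 12 weeks merely lacks a definition.

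**Nothing is decided on these results.** This also stands. Section 2.4 asks only that an economic evaluation be feasible and sets no cost or QALY threshold. A reader might infer that the progression decision is at risk; it is not. Relevance comes from the methods objective alone.

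**Conclusion.** Both parts hold, within limits. (a) The test and adjustment attached to total cost in section 4.2.d cannot be run on the quantity defined there. The defect is confined to that definition and its test, and correcting it changes no cost estimate. (b) The missing baseline-utility adjustment is a real omission whose repair costs nothing and gains precision: a standard error about 40%, 49% or 61% smaller than that of the unadjusted area-under-the-curve difference, under equal SDs and assumed r of 0.3, 0.5 or 0.7. If change from baseline were meant instead, the gain would be only about 18%, 12% or 6%.

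Neither extreme about conclusiveness is supported. Adjustment would generally leave the study imprecise: at an assumed SD of 0.10 the half-widths of 0.0063 to 0.0084 QALY all exceed the 0.0035 to 0.0058 QALY implied by the quoted utility difference. That is not true of every plausible input, since at SD 0.08 and r = 0.7 the half-width is about 0.0050. The utility SD and correlation are assumptions throughout. The point is worth correcting because this study is meant to test economic methods for the full trial.

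**What to change.** In section 4.2.d, define total cost for each patient as the sum of all cost categories to week 12. Make the between-group comparison and the covariate adjustment on those values, with the bootstrap 95% confidence interval as the main result; a t test on the same values may stay alongside. Keep mean × n group totals as description only.

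In section 4.2.c, state that the QALY difference will be estimated by regressing QALY on arm and baseline SF-6D utility. Run this within the same bootstrap, resampling patients within arm so that each patient's cost and QALY stay together. Add one line saying that QALY gained means the difference from usual care in area-under-the-curve QALYs to week 12.

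Cost: a few sentences in sections 4.2.c and 4.2.d. Baseline utility and per-patient resource use are already collected, so no extra data, visits or patients are needed.

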4.3. ACP process Evaluation

Participants will be followed for 12 months (or until bereavement, if earlier) from enrolment in the study.

Five focus groups will be conducted with HSCT staff (see below), to elicit their experience of ACP and their views on barriers and facilitators of implementation. Staff will be recruited based on their close involvement in the ACP process and identified and contacted

1. Four intervention facilitators
2. Four peer supporters
3. Four members of medical staff
4. Four members of nursing/AHP staff

5. Those training staff in ACP

Staff will be recruited based on their close involvement in the ACP process. Initially, they will be identified and contacted by co-investigators employed in the participating HSC Trusts.

Interviews will also be conducted with 4 patients and their nominated relative/friends to examine their experiences of ACP 12-weeks post-intervention. Researcher's will also observe staff training for ACP; carry out documentary analysis; and develop a process map⁴⁷ of the personnel and systems involved in managing ACP.

4.3.a. Outcome Measures from the Process Evaluation

The proportion of patients who die during the study will be recorded. This will include whose end of life wishes were complied with, as measured by a comparison of their ACP and the record of the circumstances of their death in their medical notes, and in a survey of bereaved nominated relative/friends, carried out at least 3 months after their death.

We will compare relative/friends, whose relative experienced care broadly in alignment with their wishes, with relative/friends of those who did not, in terms of their satisfaction with care, as measured by the After-Death Bereaved Family Interview⁴⁸ and level of depression measured by the Patient Health Questionnaire (POQ9)⁴⁹.

4.4. Analysis of observational data

Interviews will be digitally recorded and transcribed verbatim. Each piece of interview and other data will be coded according to the initial theory derived from CFIR and the realist review to allow indexing and retrieval in a suitable database. The documentary evidence, process map, and interview transcripts will be reviewed searching for configurations that support, contradict and link theory, seeking to explain outcomes.

4.5. Overall Outcomes and Outputs

Immediate outcome of this study will be an appraisal of the feasibility of a full study, with an analysis of the factors crucial to successful implementation of ACP, paving the way for a future definitive evaluation of the impact of ACP on the well-being of patients with complex co-morbidities and their

families, and identification of the key factors leading to successful implementation. The full study will evaluate the impact of ACP on patients who have ESKD and on associated costs, with anticipated benefits of greater adherence to their wishes at the end of life; reduced rates of hospital admission; greater use of hospice and palliative care services; less anxiety and depression; increased perception of shared decision-making; and greater well-being, and physical and social functioning. Relative/friends should experience greater agreement with patients' wishes, greater satisfaction with care, and less depression on bereavement.

4.6. Data Management

Patients will only be identifiable by their participant code – all identifying personal information will be stored in a locked filing cabinet, in a locked room. Access to study data will be restricted to the minimum number of individuals necessary for quality control and analysis – the PI and the researchers. Outside of the direct care team, only the PI and the researchers will have access to participants' personal data. A password system will be utilised to control access and passwords will be changed on a regular basis. Participant files are to be stored in numerical order and will be retained in storage for a period of 5years following study completion. Digital data will be stored on a password protected central server accessed through a password protected computer at the School of Nursing and Midwifery, Queen's University. Belfast. Checks will be applied at the time of data entry into a specific field and before the data is written (committed) to the database. Data will be analysed by members of the research team in Queen's University Belfast, Kings College London, and (in the case of data for the economic evaluation) the University of Sydney. All data will be anonymised before it is transferred or analysed. We will use the secure 'DropBox' facility provided by Queen's University to transfer password protected data files. Hard copies of documents containing research data will be stored in a locked filing cabinet in a locked room at the School of Nursing and Midwifery. Only PO will have access to this data. Tapes from interviews and focus groups will be destroyed after the data has been transcribed and recorded verbatim. Researchers will send weekly email reports to the PI with any information on missing data, missing forms, and missing visits.

5. Ethics and dissemination

Research Ethics has been granted from QUB research governance and from Belfast and Northern Trusts. Any amendments to the protocol which may affect the conduct of the study, benefits to patients, including changes to the study design, study objectives, patient population and sample sizes, procedural details will require a formal amendment to REC body. Informed consent for both participants and patients will be obtained by ACP nurses on both sites. All trial-related information will be stored securely at the Medical Biology Centre, Queen's University, Belfast (please see 4.6 for further information). Governance of the study will be guided by a Trial Management Committee and a Steering Committee. The Trial Management Committee will meet at least monthly and will oversee day-to-day aspects of the trial. It will be chaired by the PI, [name], and include the two PDRF, and other CI's as issues of particular relevance to their expertise are to be discussed, with increased input from the trial statistician during the analysis phase of the trial. The Trial Steering Committee will be chaired by [name] (Professor of Nursing Research, University of Ulster) and will comprise the PI and all the CI. It will meet in full face to face twice during the trial and there will also be two other meetings, which might take place by teleconference. The two face-to-face meetings will be near the beginning and the end of the funding period, to approve the final set-up plans for the trial and to consider the findings, prepare a publication and other dissemination activities, and plan the main trial and its funding application. The Trial Steering Committee will determine whether or not the trial has met the criteria to show that a main trial is feasible. The PI's and CI's have no competing interests to share for the overall trial and each study site.

6. Appendices

